4.3.8. Handling of Outliers

There will be no exclusion of outliers, all measured values will be included in the analyses.

4.3.9. Stratification Factors

Not applicable.

4.4. Presentation of Results

4.4.1. Presentation of Treatment Groups

Results will be presented by treatment group:

- GLPG3970 400 mg qd
- Placebo

In the Subject Information, a grand total “All Subjects” will be added to summarize all subjects over all treatment groups in tables.

4.4.2. Calculation of Descriptive Statistics

For continuous parameters, descriptive statistics will be presented when $N \geq 2$. When $N = 1$, the observation will not be shown in tables nor in figures of summary statistics but will only be listed.

Descriptive statistics will include:

- the number of non-missing data points (n);
- the arithmetic mean;
- the standard error (SE) and standard deviation (SD);

- the median, minimum and maximum;
- 90% confidence interval (CI) of the mean (if indicated in the relevant section).
- Some parameters namely hsCRP, cytokines (IL-10 and TNF α) and metabolic parameters (fasted insulin, HOMA-IR and HbA1c) are known to deviate heavily from the normal distribution but follow the log-normal distribution well. For these parameters, the geometric mean (GeoMean), geometric standard deviation (GeoSD), and geometric standard error (GeoSE) will be also reported for the summaries by treatment group and visit. GeoMean, GeoSD and GeoSE are not applicable for the summaries of the changes from baseline, however GeoM, GeoSD and GeoSE will be reported for the summaries of percent changes from baseline. This will be done by obtaining the mean, GeoSD and GeoSE of $\log(\text{value}) - \log(\text{baseline})$ and then transforming these statistics back to the 'percent change scale' as $100 \times \{\text{exponential}(\text{statistic}) - 1\}$.

For PK data, descriptive statistics will include:

- the number of non-missing observations (n);
- the number of data points above the LLOQ;
- the arithmetic mean;
- SE and SD;
- the median, minimum and maximum;
- the coefficient of variation (CV%);
- the geometric mean and geometric CV%.

If less than 50% of the subjects have quantifiable values, only the number of subjects with data, number of data points above the LLOQ, the arithmetic mean, median, minimum, and maximum will be presented with the original calculated value. The other descriptive statistics will be listed as "NC" (not calculated).

If the calculated descriptive statistic is BLOQ, then it will be presented as "BLOQ".

Individual values and descriptive statistics of concentrations and PK parameters will be presented with 3 significant digits.

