	
HbA1c) are known to deviate heavily from the normal distribution but follow the log-normal distribution well. For these parameters, the geometric mean (GeoMean), geometric standard deviation (GeoSD), and geometric standard error (GeoSE) will be also reported for the summaries by treatment group and visit. GeoMean, GeoSD and GeoSE are not applicable for the summaries of the changes from baseline, however GeoMean, GeoSD and GeoSE will be reported for the summaries of percent changes from baseline. This will be done by obtaining the mean, SD and SE of $\log(\text{value}) - \log(\text{baseline})$ and then transforming these statistics back to the 'percent change scale' as $100 \times \{\exp(\text{statistic}) - 1\}$."

	
Section 6.1.8: section added for additional listing "Procedure"

	
SAP:
 
Section 6.2.3.11.2: the paragraph starting from "The analysis of percent change from baseline..." updated as below
 
"The analysis of percent change from baseline will be performed by analyzing the $\log(\text{value}) - \log(\text{baseline})$ and transforming statistics back to the 'percent change scale' as $100 \times \{\exp(\text{statistic}) - 1\}$. The analysis of percent change from baseline up to week 6 will use the same method as for analysis of the primary efficacy endpoint as detailed in section 6.2.2.2. The GeoMean (./÷ GeoSE) of the actual values and percent changes from baseline will be presented graphically over time."

	
SAP section 6.3.2.9: updated this section to include "Profile line plots by subject of all actual observed values using relative day (ADY) will be presented by treatment group"
 
TLF Mock: MGSFLB01: Figure for lab parameters of actual values over time added'

	
SAP section 6.3.3.4: updated this section to include "Profile line plots by subject of all actual observed values using relative day (ADY) will be presented by treatment group"

		
TLF Mock: MGSFEG01: Figure for ECG parameters of actual values over time added'
 
SAP Section 6.5.2:
   
		
SAP Section 6.3.3.4:
 
Section updated to include the following text:
 
“A line plot by subject of the change from baseline will also be provided by treatment group.”
          

LIST OF ABBREVIATIONS

ACR	American College of Rheumatology
AE	adverse event
ALT	alanine aminotransferase
AST	aspartate aminotransferase
ATC	anatomical therapeutic chemical
AUC	area under the plasma concentration-time curve

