2.2.3. Other Endpoints

2.3. Study Design

This is a Phase 2, randomized, double-blind, placebo-controlled, multicenter parallel-group study evaluating GLPG3970 in adult subjects with moderately to severely active RA and an inadequate response to MTX. In this study, subjects will receive 1 dose level of GLPG3970 (400 mg once daily [q.d.]) or placebo on top of their stable dose and dosing regimen of MTX.

The study is planned to randomize 25 subjects in a 3:2 ratio (15 subjects planned to receive GLPG3970 and 10 subjects planned to receive placebo).

The study will consist of 3 study periods:

[figure not shown]
- Screening period: up to 3 weeks with 1 study visit.
- Double-blind treatment period: 6 weeks with 4 study site visits (Days 1, 15, 29, and 43) and 1 telephone call (Day 8).
- Follow-up (FU) period: 2 weeks with 1 study visit.

Subjects will participate in the study for a maximum of 11 weeks (screening to FU) and will receive oral GLPG3970 or placebo, as a reconstituted oral solution, q.d. for 6 weeks.

Refer to the Schedule of Assessments (Section 2.5) for further details.

A schematic diagram of clinical study design, procedures and stages is provided in [Figure 1](#).

Figure 1 Schematic Diagram

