2.6. Sample Size Justification

The operating characteristics of the chosen decision framework at a sample size of 15 subjects (GLPG3970) + 10 subjects (placebo) are represented in the following graphical output and table, and were deemed acceptable. A common standard deviation (SD) of 1.3 for placebo and GLPG3970 was assumed based on previous experience with RA studies.

Lower Reference Value (LRV) and Target Value (TV) for the decision framework were determined based on the published studies and the therapies in development or on the market. They were identified by the project team as the lowest delta of possible interest and the best case scenario for efficacy outcome respectively.

A dropout rate of 20% was taken into account to allow a minimum of 20 subjects to complete the study. In case of drop-outs due to SARS-CoV-2 infection, additional subjects may be randomized on top of the planned sample size. The number of additional subjects randomized will not exceed the number of subjects dropping out of the study in relation to SARS-CoV-2. Randomization of additional subjects will ultimately be decided by the sponsor before any study lock or related unblinding has occurred.

Probability	Reference value	Outcome
0.852	-1.6	Signal detected
0.043	-1.6	No conclusion
0.105	-1.6	No signal detected
0.192	-0.6	Signal detected
0.091	-0.6	No conclusion
0.717	-0.6	No signal detected

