6.5.2. Presentation of Results

All continuous parameters mentioned in section 6.5.1 will be summarized by means of descriptive statistics (including 90% CI of the mean change from baseline) by treatment group and analysis window. Actual values, changes from baseline and percent change from baseline will be tabulated separately.

Between-group comparisons will be based on the percent change from baseline, and will present a p-value and 90% CI of the delta between GLPG3970 and placebo. The same MMRM approach as for the efficacy endpoints will be applied.

Graphs of the mean (+- SE) actual values over time and of the mean (+- SE) change from baseline, and percent changes from baseline will be presented for all continuous parameters. Also, linear-linear plots for actual values will be provided by treatment group. In addition, profile line plots of the percent change from baseline will be provided by treatment group.

For cytokines and metabolic markers mentioned under section 6.5.1, the analysis of percent change from baseline will be performed as described in section 4.5.2. The same MMRM approach as detailed in [section 6.5.1.2](#) will be applied. The GeoLSM and GeoSE and corresponding 90 % CI will be presented (the same back transformation to the 'percentage scale' as for the geometric descriptive statistics will be applied to the LS-mean, SE and corresponding 90% CI bounds). The GeoMean (\cdot/\div GeoSE) of the actual values and percent changes from baseline will be presented graphically over time on a log-linear scale. Error band will be calculated as follows:

- Error bands: $100 \times [\text{exponential} \{ \text{mean} (Z) \pm \text{SE} (Z) \} - 1]$. Where $Z = \log (\text{value}) - \log (\text{baseline})$.

Listings will be provided for all cytokines, bone markers and metabolic markers separately. Column includes the actual values, change from baseline and percent change from baseline, and also a flag for high/low values in case a normal range exists.

Note: HOMA-IR values will be excluded from analysis if samples are not taken fasted (i.e. "fasted" is explicitly mentioned in the database),

6.6.

[REDACTED]

[REDACTED]

[REDACTED]

[REDACTED]

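### SAP 4.4.2: on the usual meaning of GeoSD and GeoSE, the rule for percent change exponentiates the spread twice and conflicts with SAP 6.5.2

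*SAP*

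**What the plan says.** SAP 4.4.2 (Calculation of Descriptive Statistics) treats hsCRP, IL-10, TNF-alpha, fasted insulin, HOMA-IR and HbA1c as log-normal. For these markers it adds a geometric mean and says that the "geometric standard deviation (GeoSD), and geometric standard error (GeoSE) will be also reported". It gives no formula for either measure of spread.

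For percent change from baseline the same bullet gives a recipe. Write Z = log(value) − log(baseline). The programmer is told: "This will be done by obtaining the mean, GeoSD and GeoSE of" Z, "and then transforming these statistics back to the" percent-change scale by 100 × {exp(statistic) − 1}. One transformation is applied to all three statistics.

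SAP 6.5.2 (Presentation of Results), on the cytokines and metabolic markers, says that the same back-transformation "will be applied to the LS-mean, SE and corresponding 90% CI bounds". It also prints a formula for the error bands of the graphs, 100 × [exp{mean(Z) ± SE(Z)} − 1]. Both use the plain SE on the log scale.

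**The concern.** A geometric SD is ordinarily the exponential of the SD of the logs, and a geometric SE the exponential of their SE. The mean of Z is still on the log scale, so a single exponentiation is right for it. A GeoSD or GeoSE has already left the log scale, so the same transformation exponentiates it a second time. In that sentence GeoSD and GeoSE are both what goes into the transformation and what is meant to come out of it.

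At stake are the GeoSD and GeoSE columns in the percent-change tables for these six markers. For the cytokines and metabolic markers, those tables would also disagree with the graphs built under 6.5.2 from the same data. For hsCRP the matching efficacy section is blacked out in the public SAP, so no such comparison can be made.

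**Working it through.** The documents print no numerical result for this formula, so there is no figure to reproduce. The check compares one exponentiation with two.

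**Inputs**
- Transformation: 100 × {exp(statistic) − 1} (SAP 4.4.2).
- Arm sizes: 15 on GLPG3970 and 10 on placebo (SAP 2.3). With the 20% dropout in SAP 2.6 spread evenly (an assumption), 0.8 × 15 = 12 and 0.8 × 10 = 8 completers.
- Meaning of GeoSD and GeoSE: exp(SD of Z) and exp(SE of Z). This is an assumption, because the SAP does not define them.
- SD of Z: not given in the documents. Values from 0.1 to 1.5 were examined.

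**Formulas.** Let s be the SD of Z, or its SE = SD/√n.
- Once: 100 × {exp(s) − 1}
- Twice: 100 × {exp(exp(s)) − 1}
- Overstatement: R(s) = {exp(exp(s)) − 1} / {exp(s) − 1}

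**Worked case, SD of Z = 0.5**
- SD, once: exp(0.5) = 1.649, giving 64.9%. Twice: exp(1.649) = 5.200, giving 420.0%. R = 6.5.
- SE at n = 15: 0.5/√15 = 0.129. Once 13.8%, twice 212.0%. R = 15.4.
- SE at n = 10: 0.5/√10 = 0.158. Once 17.1%, twice 222.6%. R = 13.0.

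**Other assumed SDs** (each cell: once / twice / R)

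| SD of Z | SD | SE, n = 15 | SE, n = 10 |
|---|---|---|---|
| 0.3 | 35.0% / 285.7% / 8.2 | 8.1% / 194.6% / 24.2 | 10.0% / 200.3% / 20.1 |
| 0.8 | 122.6% / 825.8% / 6.7 | 22.9% / 241.9% / 10.5 | 28.8% / 262.5% / 9.1 |
| 1.0 | 171.8% / 1415.4% / 8.2 | 29.5% / 265.0% / 9.0 | 37.2% / 294.3% / 7.9 |
| 1.5 | 348.2% / 8738.4% / 25.1 | 47.3% / 336.2% / 7.1 | 60.7% / 398.8% / 6.6 |

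**Bounds**
- Minimising R(s) numerically gives 6.31 at s = 0.61. This floor holds for any SD or SE.
- As s falls to zero, the twice-exponentiated value tends to 100 × (e − 1) = 171.8%. A marker with almost no variability would still show a spread above 171.8%.
- R reaches 10 at s = 0.222 on the low side. For the SE this means SD of Z ≤ 0.222 × √n: 0.86 at n = 15, 0.77 at n = 12, 0.70 at n = 10 and 0.63 at n = 8.
- R also exceeds 10 above s = 1.126. For an SE that needs an SD of Z of at least 1.126 × √8 = 3.18 even in the smallest group, well outside the range examined.

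**The case against.** The strongest reply is that this is a labelling slip that would mislead nobody. The sentence pairs a plain mean, not a geometric mean, with GeoSD and GeoSE, and it speaks of transforming back, which makes sense only for quantities still on the log scale. SAP 6.5.2 prints the single-exponentiation formula. The version-history entry describing this insertion reads "This will be done by obtaining the mean, SD and SE of" the log ratio. That entry is not the current text and its difference from 4.4.2 is not itself an error, but it does suggest the intent. The SAP introduction also places technical derivation details in a separate document that is not public. If GeoSD and GeoSE were loosely meant as the log-scale SD and SE, nothing is exponentiated twice.

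Most of this stands as evidence of intent. It does not remove the defect: 4.4.2 is the only visible place where the descriptive derivation is written, it spells the terms out as geometric quantities in the same bullet, and it does not match 6.5.2.

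Four stronger readings are tempting and are not supported:
- **The SE is always overstated 10-fold or more.** It is not. At an SD of Z of 0.8 the factor is 9.1 for 10 subjects and 8.5 for 8.
- **The GeoSD cannot be computed when a marker falls.** That requires taking the logarithm of Z itself, which is a different definition from the one behind the figures above. The two arguments cannot be combined.
- **SAP 6.5.2 repeats the error.** It applies the transformation to the plain SE, which is one exponentiation. It is the passage that 4.4.2 contradicts.
- **The biomarker conclusions are compromised.** The between-group estimates, their intervals and p-values do not pass through this rule. Three of the six markers are metabolic parameters, which the protocol's account of the mechanism does not name.

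**Conclusion.** The point holds as a wording error with a numerical consequence. On the usual meaning of GeoSD and GeoSE, SAP 4.4.2 exponentiates the spread of percent change twice, in conflict with SAP 6.5.2. The overstatement is then at least about 6.3-fold for the SD and for the SE, with no assumption about the true spread. A factor of 10 or more for the SE depends on an SE of Z of about 0.22 or less, and the documents give no log-scale SD from which to judge that.

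The size rests entirely on the assumed definition of the two terms. The scope is narrow: descriptive GeoSD and GeoSE of percent change only. This is a minor correction, worth making because the figures would be uninterpretable if the rule were programmed as it stands.

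**What to change.** In SAP 4.4.2, replace GeoSD and GeoSE by SD and SE in the sentence that defines the calculation, so that the mean, SD and SE of log(value) − log(baseline) are obtained and each is back-transformed once. This agrees with 6.5.2, which needs no change on this point. If the separate derivation document repeats the rule, check it against the corrected sentence.

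The cost is two words in the SAP. No data, design feature or other analysis changes.

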4.4.3. Calculation of Percentages

Frequencies and percentages will be generated for categorical parameters.

For event-type data (e.g. AEs), the denominator will be all subjects in the analysis set and analysis period. For other data (e.g. worst-case analysis of assessments), the denominator will be all subjects with (post-baseline) data for the parameter, in the analysis set and analysis window/period.

5. INTERIM ANALYSES AND INTERNAL DATA SAFETY MONITORING COMMITTEE

No formal interim analysis is planned for this clinical study.

An internal SMC independent from the study will review unblinded safety data during the course of the study. This Committee may involve external medical experts (such as an expert in the field of RA and an infectious diseases expert) to support data interpretation. The Committee will review unblinded safety data and assess any potential safety issues arising during the conduct of the clinical study, including (but not limited to) any potential issues in the context of the SARS-CoV-2 pandemic. The clinical study team will remain blinded to the allocation of subjects to treatments during the course of the study. The process is described in a separate 'SMC Charter'.

6. STATISTICAL ANALYSES

6.1. Subject Information

Subject information will be tabulated using the Safety Analysis Set, unless specified otherwise. No inferential testing will be performed, nor will p-values be provided.

Subject information will be tabulated with descriptive statistics per planned treatment group, as well as overall.

6.1.1. Demographic and Baseline Disease Characteristics

The following parameters will be summarized:

- date of ICF signature (listed);
- sex;
- age at signing the ICF (years);
- age, categorized (years): $18 \leq \text{age} < 65$; $65 \leq \text{age} < 85$; $\text{age} \geq 85$;
- race and ethnicity;
- height at baseline (cm);
- weight at baseline (kg);
- body mass index (BMI) at baseline (kg/m^2) =
$$\frac{\text{weight} \ (\text{kg})}{\text{height}^2 \ (\text{m}^2)}$$
(BMI will not be recalculated if already available in the database);
- duration of RA (years)
$$= \frac{(\text{date of first study drug administration}) - (\text{date of initial diagnosis}) + 1}{365.25}$$

If missing day: use 1st day of the month

If missing both day and month: use 1st of January;

- Duration of RA, categorized (years): < 1 ; $1 \leq \text{duration} < 5$; $5 \leq \text{duration} < 10$; $10 \leq \text{duration} < 15$; $15 \leq \text{duration} < 20$; $\text{duration} \geq 20$;
- hsCRP (mg/L) at baseline;

- DAS28 (CRP) at baseline;
- [REDACTED]
- [REDACTED]
- TJC68 and SJC66 joint counts;
- [REDACTED]
- [REDACTED]
- [REDACTED]

Demographic and baseline disease characteristics will be listed.

6.1.2. Allocation and Randomization

The number of subjects (and percent) per treatment group and overall will be tabulated per country and site.

The following listings will be provided:

- Listing per subject of the IP kit numbers, IP lot numbers dispensed/returned.
- Randomization schemes and codes, with the treatment assigned to each subject. This listing includes a flag in case of discrepancies or errors between the assigned and the actual treatment taken, and should also include flags declaring any (potential) unblinding.

6.1.3. Disposition Information

The following tabulations will be provided, by treatment group and overall:

- The number of subjects screened, not-randomized (including reasons), randomized (treated and not treated), and treated with GLPG3970 and Placebo.
- Number (percent) of subjects randomized per country and site.
- The number (percent) of subjects in each analysis set as defined in Section 4.1.
- The number (percent) of subjects per analysis window as defined in Section 4.3.3.
- The number (percent) of subjects who completed/discontinued the IP administration schedule and the reasons for discontinuation.
- The number (percent) of subjects who completed/discontinued the study and the reasons for discontinuation.

Discontinuation related to SARS-CoV-2 will be flagged in the listing.

Additionally, the following information will be provided in listings:

- Subject identification and randomization (country, site number, investigator, subject number).

- Randomization number and date, planned and actual randomization group, with flags for any discrepancies.
- Subjects excluded from the safety and full analysis sets, including reasons.
- First and Last Key Dates in the Study will be listed

6.1.4. Protocol Deviations and Eligibility

Major protocol deviations are determined and recorded while the study is ongoing, and the list is finalized prior to database lock (and unblinding). For more details, please refer to the Protocol Deviations Plan.

The number (percent) of subjects with major protocol deviations will be tabulated, overall and per class of deviation, by treatment group and overall.

All available information concerning major protocol deviations, including COVID-19 related verbatim, violations on eligibility criteria and subjects not treated will be listed. Protocol deviations leading to the exclusion of subjects from any analysis set, as applicable, will be flagged.

Minor protocol deviations will not be tabulated and will not be listed.

6.1.5. Medical History and Concomitant Diseases

Frequency tabulations, per treatment group and overall, per system organ class and preferred term will be provided for the medical history findings (i.e., conditions no longer present at the start of the study) as well as for the concomitant diseases (i.e. conditions present at the start of the study) using Medical Dictionary for Regulatory Activities (MedDRA) coding dictionary.

All medical history findings and concurrent diseases will be listed separately.

6.1.6. Rheumatoid Arthritis Disease History (RA)

Frequency tabulations, per treatment group and overall, per system organ class and preferred term will be provided for the RA disease history using MedDRA coding dictionary.

All RA disease history will be listed.

6.1.7. Prior and Concomitant Medications

6.1.7.1. Coding of Reported Terms

All prior and concomitant medication terms will be coded in the database using the World Health Organization (WHO) drug coding dictionary.

6.1.7.2. Classification of Medications

All prior and concomitant medication records will be categorized as follows, considering their date and flags indicating the relative timing versus study (drug) start or end (before, after, ongoing):

- Prior only: when the record ended before the first IP administration date.
- Concomitant only: when the record started on or after the first IP administration date.
- Prior and concomitant: when the record started before the date of first IP administration, and ended on or after this point, or continued.

When the start or end date of the prior and concomitant medication records are incomplete (and no flags indicating relative timing are available), the date of first IP administration will be considered to the same level of information provided by these incomplete dates to categorize the timing of these records. This means that a record only having month and year will be categorized comparing only to the month and the year of the date of first IP administration.

